ABC-C	Aberrant Behavior Checklist – Community
AE	adverse event
AED	anti-epilepsy drug
Allo-S	Allopregnanolone Sulfate
ALT	alanine aminotransferase
ANOVA	analysis of variance
AST	aspartate aminotransferase
ATC	Anatomical Therapeutic Chemical
bpm	beats per minute
BMI	body mass index
BRIEF	Behavior Rating Inventory of Executive Function
BUN	blood urea nitrogen
CGI-C	Clinical Global Impression of Change
CGI-I	Clinical Global Impression of Improvement
cm	centimeter
CO2	carbon dioxide
CRF	case report form
CSHQ	Children's Sleep Habit Questionnaire
D/C	discontinuation
DB	double-blind
DMC	Data Monitoring Committee
ECG	electrocardiogram
EEG	electroencephalogram
eCRF	electronic case report form
°C	degrees Celsius
FDA	Food and Drug Administration
GNX	ganaxolone
ICH	International Conference on Harmonization of Technical Requirements for Registration of Pharmaceuticals for Human Use
IP	investigational product
ITT	intent-to-treat
IWRS	Interactive Web Response System
kg	kilogram
kg/m ²	kilogram per square meter
LAR	legally authorized representative

Abbreviation	Term
lb	pound
LLN	lower limit of normal
m	meter
MedDRA	Medical Dictionary for Regulatory Activities
mg	milligram
mmHg	millimeters mercury
OL	open-label
OLE	open-label extension
PBO	placebo
PCDH19	protocadherin 19
PedsQL-FIM	Pediatric Quality of Life Inventory – Family Impact Module
PK	pharmacokinetics
PP	per protocol
PT	preferred perm
QI	Quality of Life Inventory
SAEs	serious adverse events
SAP	statistical analysis plan
SD	standard deviation
SI	Système International
SOC	system organ class
TEAE	treatment-emergent adverse event
ULN	upper limit of normal
US	United States
WHO	World Health Organization
wks	weeks

1 INTRODUCTION

The purpose of this statistical analysis plan (SAP) is to describe the procedures and the statistical methods that will be used to analyze and report results for Protocol 1042-PCDH19-3002 (Version 6.0, Protocol Amendment 5, 20 January 2021). This statistical plan does not include the analyses of the pharmacokinetic and pharmacodynamic (exposure response analysis) data.

The structure and content of this SAP provides sufficient detail to meet the requirements identified by the Food and Drug Administration (FDA) and International Conference on Harmonization of Technical Requirements for Registration of Pharmaceuticals for Human Use (ICH): Guidance on Statistical Principles in Clinical Trials.¹ All work planned and reported for this SAP will follow international accepted guidelines published by the American Statistical Association² for statistical practice.

The following documents were also considered in preparation for writing this SAP:

- International Conference on Harmonization (ICH) E3 Guideline: Structure and Content of Clinical Study Reports³
- ICH E6 Guideline on Good Clinical Practice⁴
- ICH E8 General Considerations for Clinical Trials⁵
- ICH E9 Statistical Principles for Clinical Trials⁶

The SAP is a supplement to the study protocol, which should be referred to for additional details on study design, study conduct, and other operational aspects of the study.

1.1 STUDY OBJECTIVES

1.1.1 Primary Objective

- To assess the efficacy of ganaxolone (GNX) compared with placebo (PBO) as adjunctive therapy for the treatment of primary seizures in children with genetically confirmed PCDH19-related epilepsy during the 17-week double-blind (DB) phase.

1.1.2 Secondary Objectives

- To assess the effect of GNX on primary seizure rate in biomarker-positive subjects.
- To assess behavioral/neuropsychiatric changes in subjects receiving GNX compared with subjects receiving PBO as adjunctive during the 17-week double-blind (DB) phase.
- To assess the safety and tolerability of GNX compared with PBO as adjunctive therapy during the 17-week DB phase.
- To assess pharmacokinetic (PK) parameters in subjects receiving GNX doses up

to 63 mg/kg/day (1800 mg/day maximum) throughout the study.

- To assess the long-term efficacy of GNX when administered as adjunctive therapy throughout the open-label (OL) phase.
- To assess the long-term safety and tolerability of GNX when administered as adjunctive therapy throughout the OL phase.

1.1.3 Exploratory Objectives

1.2 STUDY ENDPOINTS

1.2.1 Primary Efficacy Endpoint

The primary efficacy endpoint is the percent change in 28-day primary seizure frequency during the 17-week DB phase relative to the baseline in all subjects. The primary seizure types are defined as countable focal seizures that include progressive hypotonia and impaired awareness, or any countable focal or generalized seizure with a clear motor component. Focal and generalized nonmotor seizures and myoclonic seizures do not count as the primary seizure types.

1.2.2 Secondary Efficacy Endpoints

1.2.2.1 Seizure Control Endpoints:

- The percent change in 28-day primary seizure frequency during the 17-week DB phase relative to baseline in biomarker positive subjects.
- Percentage of subjects experiencing a $\geq 50\%$ reduction in 28-day primary seizure frequency compared to baseline.

1.2.2.2 Behavioral/Neuropsychiatric Endpoints

- Behavior Rating Inventory of Executive Function (BRIEF, preschool version BRIEF-P)
- Aberrant Behavior Checklist – Community (ABC-C)

- Children's Sleep Habit Questionnaire (CSHQ)

1.2.3 Exploratory Efficacy Endpoints

1.2.4 Pharmacokinetic Assessments

- Pharmacokinetic concentrations

The samples will be drawn between 1 and 5 hours or between 4 and 8 hours after the last dose during the double-blind and open-label periods.

1.2.5 Safety and Tolerability Endpoints

- Vital signs: blood pressure [BP], heart rate [HR], respiratory rate [RR], body temperature, weight, and height.
- Electrocardiograms (ECGs).
- Clinical laboratory tests - hematology, chemistry, and urinalysis.
- Physical, neurological, and developmental examinations.
- Concomitant Anti-Epilepsy Drug (AED) levels.
- Concomitant medications and therapies.
- Frequency, type and severity of adverse events (AEs)

1.2.6 Open-Label Extension Phase Endpoints

Except for the changes in seizure frequency during the titration portion and during the maintenance portion, the same efficacy, exploratory, quality of life, and safety endpoints for the DB phase will also be used for the OL phase. Analyses of OL phase data will be summarized separately.

1.3 STUDY DESIGN

1.3.1 General Study Design and Plan

This is a global, biomarker-stratified, DB, randomized, PBO-controlled trial of adjunctive GNX treatment of primary seizures in female children with a confirmed pathogenic or likely pathogenic PCDH19 mutation. The trial consists of a prospective baseline period of 8 to 12 weeks in duration to collect seizure data, followed by a 17-week DB treatment phase, which is then followed by a long-term OL phase (Figure 1). An interactive web response system (IWRS) will be used to randomize subjects, dispense drug, track treatment, and maintain the blind throughout the duration of the study.

[figure not shown]
During the screening visit, each subject's allopregnanolone sulfate (Allo-S) biomarker level will be assessed via a blood draw and subsequent analytical quantification. Each subject will then be assigned to 1 of 2 groups: biomarker-positive or biomarker-negative. A subject will be considered biomarker-positive if the baseline Allo-S level is less than or equal to 2500 pg/mL (Pinna Lab method or similar). A subject with a baseline Allo-S level greater than 2500 pg/mL will be classified as biomarker-negative. The biomarker group assignment will remain blinded until database unblinding. Based on the 11-subject

OL study, it is estimated that approximately 65% of subjects will be biomarker-positive.

The DB phase includes 4 weeks of investigational product (IP) titration followed by 13 weeks of dose maintenance. After meeting the eligibility criteria, approximately 25 children aged 1 to 17 years (inclusive) with PCDH19-related epilepsy will be randomly assigned to receive GNX or PBO (1:1 ratio within each biomarker stratum) for 17 weeks in addition to their standard anti-seizure treatment. Subjects will be titrated to 63 mg/kg/day (max 1800 mg/day) over 4 weeks and then maintained at that dose for another 13 weeks. Subjects who are not able to tolerate 63 mg/kg/day (or 1800 mg/day maximum) may be maintained on a lower dose. A minimum dose of 33 mg/kg/day or 900 mg/day is generally required following the DB escalation period, unless a lower dose is agreed to with the sponsor due to the tolerability such as somnolence. At each visit, dosing will be reviewed and adjusted as needed based on subject's current weight.

Subjects who discontinue IP treatment before the completion of the DB phase will continue to be followed per protocol and, at a minimum, subjects will be encouraged to maintain daily seizure eDiary entries until the DB phase is completed. These subjects will also return to the site 2 to 4 weeks after the taper for safety follow-up post-taper assessments.

After completing the initial 17-week, DB, PBO-controlled phase, all subjects will be treated with GNX in the OL phase of the study. Ganaxolone subjects will continue GNX treatment and PBO subjects will titrate onto GNX. To maintain the blind, subjects initially randomized to GNX will undergo a blinded titration (increasing PBO doses) for 4 weeks, whereas PBO subjects will titrate up to 63 mg/kg/day GNX (1800 mg/day maximum) during the same time period. Any subject who completes the study or discontinues IP treatment at any time during the study should undergo a 2-week drug de-escalation (taper) period and return to the site 2 weeks later for safety follow-up post-taper assessments. Taper is not required if the subject is receiving the dose of 18 mg/kg/day or 450 mg/day (or lower).

Figure 1. Study Design

Subjects will be required to complete an eDiary to determine the effect of GNX on drug-resistant seizures. An electronic eDiary is the standard. In rare cases when an eDiary completion is not feasible, a paper diary will be used. These cases will need approval by the sponsor. A variety of clinician- and caregiver- administered instruments will be used to assess the efficacy of adjunctive GNX in PCDH19, and will include the following:

- Behavior Rating Inventory of Executive Function (BRIEF)
- Aberrant Behavior Checklist – Community (ABC-C)
- Children’s Sleep Habit Questionnaire (CSHQ)
- Pediatric Quality of Life Inventory – Family Impact Module (PedsQL-FIM)
- Quality of Life Inventory – Disability (QI-Disability)
- Caregiver Global Impression of Change (CGI-C) – Target Behavior, Clinical Global Impression – Improvement [caregiver], and Clinical Global Impression – Improvement [clinician].

Safety and tolerability will be assessed by monitoring vital signs (blood pressure [BP], heart rate [HR], respiratory rate [RR], body temperature, weight, and height); 12-lead ECGs, clinical laboratory tests (hematology, chemistry, and urinalysis); physical, neurological, and developmental examinations; and frequency, type, and severity of AEs during the 17-week, DB phase and the OL phase.

The Schedule of Assessments for the 17-week pre-randomization and DB phase and for the OL is presented in the Appendix 14.1.

1.3.2 Sample Size and Power Considerations

A total of 50 subjects (25 in each treatment group) was planned to be enrolled in the

study.

As indicated in Protocol Amendment 4, Version 5 (dated 30 June 2020), enrollment in the study was discontinued early due to administrative reasons. As a result, the final sample size is not based on statistical considerations. Formal hypothesis testing will be performed based on all available sample size at the time of the study discontinuation.

2 STATISTICAL METHODS

2.1 GENERAL CONSIDERATIONS

In general, non-categorical variables will be summarized by number of subjects, mean, standard deviation (SD), median, 25th and 75th percentiles, minimum, and maximum values. Categorical variables will be summarized by counts and percentage of subjects in each category.

Except where noted, separate tables and data listings will be prepared for the DB and OL phases of the study. Only events occurring before entry into the OL phase will be included in the DB phase outputs, and except where indicated, only baseline events and events occurring after entry into the OL phase will be included in the OL phase outputs.

Tables will be provided using the intent-to-treat (ITT) subject population as well as within each of the biomarker positive and biomarker negative strata. The within-stratum placebo group will consist of only the subjects within the corresponding stratum. The tables for the DB phase will show the results for each DB treatment group, and, where noted, combined over the groups as well. The tables for the OL phase, during which all subjects will be receiving GNX, will show the results by assigned DB treatment group and for all OL subjects combined. For the efficacy endpoints, the results will be derived according to the randomized treatment group; for the other endpoints, data will be analyzed according to the treatment actually received. As such, any subject randomized to receive PBO but taking at least one dose of GNX will be reported in GNX group.

Source data for the summary tables and statistical analyses will be presented as subject data listings, which include data collected on the electronic case report forms (eCRFs) as well as any derived efficacy variables for all randomized subjects.

Baseline seizure activity will be determined by the subject's daily seizure eDiary entries for the 8 or 12 week period immediately prior to Visit 2 (Day 0), depending on eligibility criteria in the applicable protocol version. For primary seizures only, if a subject's baseline seizure count from this prospective baseline period is less than 4, the primary seizure count from the Historical Seizure Calendar Review CRF will be used to calculate a baseline 28-day seizure count. Within the DB phase of the study, determination of post-baseline seizure activity will begin on the day following the first day of DB treatment. The first day of DB treatment (Day 0) is included in neither the baseline nor DB phase since seizures could occur both before and after the initiation of treatment. Determination of post-baseline seizure activity assigned to the OL phase will begin on the day following the first OL treatment.

Baseline values for non-seizure efficacy and safety assessments are defined as the last non-missing value of the assessment before the first dose of treatment.

The OL phase will use the same baseline as the DB phase.

The study day for all assessments that are performed on or after the first day of treatment will be calculated as:

$$\text{Study Day} = \text{date of the assessment} - \text{date of first treatment} + 1.$$

For assessments performed before the first day of treatment, the study day calculation is:

$$\text{Study day} = \text{date of the assessment} - \text{date of first treatment}.$$

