7.2 OPEN LABEL EXTENSION

All of the analyses for the DB phase will be repeated for the OL phase, with the following differences:

- All results will only be summarized descriptively.
- The results will be presented overall and classified according to the DB treatment received by the subjects
- The post-baseline seizure endpoints will be derived based on the first full day of OL treatment (one day after OL start).
- No sensitivity analyses will be performed.
- Analyses of seizure frequencies during titration and maintenance phases are only applicable to the DB phase and will not be included in the OL phase analyses.
- The time points for the efficacy, exploratory, and quality of life endpoints will be after 19 weeks, 51 weeks, and every 16 weeks thereafter of open-label treatment relative to the prospective baseline phase.
- The differences between the DB treatment groups in the percent changes from baseline of the 28-day seizure frequencies will not be tested for statistical significance.

- No PP analyses will be performed.

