9 SAFETY ANALYSIS

All safety analyses will be performed in the Safety Population. The results in the DB and OL phases will be summarized separately. In both phases, the results will be summarized by the DB treatment actually received and, for the OL phase of the study, combined over the treatment groups. Baseline for safety endpoints is defined as the last non-missing value obtained before the first day of DB treatment. Assessments performed at multiple post-baseline time points will be summarized at each time point for which they are scheduled, but the listings will also include any assessments performed at unscheduled time points.

The number and percentage of days that subjects received investigational product, the highest percentage of the maximum allowable daily dose (1800 mg or 63 mg/kg) that subjects received, and the total amount of investigational product received will be summarized. For the OL phase, they will be summarized over just the OL phase as well as over the entire study (combined DB and OL phases) but the classification by the DB treatment applies only for the OL phase summary. The summarization over the entire study will include only subjects who were in the GNX group during the DB phase, regardless of whether they entered the OL, and all the subjects from the OL phase. A subject data listing will be provided with full details of the study drug dispensation.

Safety assessments include:

- AEs
- Clinical laboratory tests
- Vital signs including BP, HR, RR, body temperature, weight, and height
- 12-lead Electrocardiogram (ECG)
- Physical, neurological and developmental examinations
- Neurosteroid levels
- Tanner staging (OL phase only)

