9.1 ADVERSE EVENTS

AEs will be coded by System Organ Class (SOC) and Preferred Term (PT) using MedDRA®, version 22.0 or higher. The verbatim term will be included in the AE listings. Except where indicated, the summary tables will include only treatment-emergent adverse events (TEAEs). All AEs, treatment-emergent or otherwise, will be

presented in subject data listings.

A TEAE is defined as an AE that starts or worsens on or after the first dosing day of study drug. The AE analyses for the DB treatment phase of the study will include AEs that start or worsen during that phase and will not include AEs that start or worsen during the OL phase; i.e., they will not include any AEs starting or worsening on or after the first dosing day of the OL phase.

For the OL phase of the study, the adverse event results will be summarized over just the OL phase as well as over the entire study (DB and OL phases) but the classification by the DB treatment applies only for the OL phase summary. The summarization over the entire study will include only subjects who were in the GNX group during the DB phase, regardless of whether they entered the OL, and all the subjects from the OL phase; i.e., it will include only the TEAEs following GNX exposure. The summarizations over just the OL phase will include TEAEs that occur or worsen on or after the first day of the OL phase; the summarizations over the entire study will include TEAEs that start or worsen on or after the first dosing day of GNX.

The TEAEs will be summarized as the number of events and the number and percentage of subjects with TEAEs. Subjects who report the same PT on multiple occasions will be counted once for the PT: under the highest severity (severe > moderate > mild) when summarized by severity and under the closest relationship (related > not related) to study drug when summarized by relationship.

If a subject reports multiple PTs for a SOC, the subject will be counted only once for that SOC. For the counting of events, all the PTs will be included in the counts, even when subjects have multiple PTs.

Non-treatment emergent AEs will only be listed.

TEAEs will be summarized as follows:

- An overview table of TEAEs, including number of events and number (%) of subjects with:
 - TEAEs
 - Serious AEs (SAEs)
 - Study drug related TEAEs
 - TEAEs by severity
 - TEAEs leading to study discontinuation
 - TEAEs leading to death
 - Adverse events of special interest (AESI)
- TEAEs by SOC and PT

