9.3 OTHER SAFETY ENDPOINTS

9.3.1 Vital Signs

Vital signs include weight (kg), height (cm), temperature (°C), systolic and diastolic blood pressure (mmHg), respiration rate (breaths per minute), and pulse rate (bpm).

Quantitative results (including actual value and change from baseline to each post-baseline visit) will be summarized using descriptive statistics by baseline and post-baseline visit for each parameter.

Listings of vital signs will be provided.

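### Open-label laboratory, vital-sign and ECG changes for former placebo subjects are measured only from the pre-placebo baseline, so they include 17 weeks without ganaxolone

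*SAP*

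**What the plan says.** SAP 2.1 sets one rule for both phases: "The OL phase will use the same baseline as the DB phase". Protocol 9.7 says the same. SAP 9 applies it to safety: "Baseline for safety endpoints is defined as the last non-missing value obtained before the first day of DB treatment". SAP 7.2 opens with "All of the analyses for the DB phase will be repeated for the OL phase, with the following differences", and none of the differences it lists is a new baseline.

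The two arms reach ganaxolone at different times. After the 17-week double-blind phase, "Ganaxolone subjects will continue GNX treatment and PBO subjects will titrate onto GNX" (SAP 1.3.1). The displays are nevertheless organised around a phase in which everyone is on drug: "The tables for the OL phase, during which all subjects will be receiving GNX, will show the results by assigned DB treatment group" (SAP 2.1). Safety results are shown by double-blind treatment received and, "for the OL phase of the study, combined over the treatment groups" (SAP 9).

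The summaries that use this baseline are:
- vital signs, including weight and height, "including actual value and change from baseline to each post-baseline visit" (SAP 9.3.1);
- laboratory change and shift tables (SAP 9.2);
- ECG change by visit (SAP 9.3.2);
- the criterion of a QTc rise of at least 60 msec (SAP 14.3.2) and the urinalysis criteria that compare with a pre-Rx value (SAP 14.3.1).

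Adverse events are handled differently. For them, "the summarizations over the entire study will include TEAEs that start or worsen on or after the first dosing day of GNX" (SAP 9.1).

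**The concern.** For a girl randomised to placebo, the last value before ganaxolone is the one at Visit 5. The open-label tables compare her later values with one taken before placebo, so her change from baseline mixes untreated and treated time.

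Classifications can be wrong in either direction. An ALT that rose above normal on placebo and stayed there counts as a normal-to-high shift in the open-label table. A value that was high before placebo, normal at Visit 5 and high again on ganaxolone shows no shift.

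Long-term safety and tolerability of ganaxolone is a secondary objective (Protocol 2.2.2, SAP 1.1.2), and these tables are part of the evidence for it. The subjects are growing children, so weight in particular moves with elapsed time whatever the treatment.

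**Working it through.** The plan gives no figure on this point to reproduce. The check is of intervals and of the data available.

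**Inputs**
- Length of the double-blind phase: 17 weeks (SAP 1.3.1).
- Open-label clinic visits: Weeks 21, 36, 52 and 68 (Protocol Table 2).
- Check on the offset: SAP 7.2 places open-label efficacy time points after 19 and 51 weeks of open-label treatment. 17 + 19 = 36 and 17 + 51 = 68, which match Visits 7 and 9.

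**Formula for a former placebo subject**, using nominal weeks: share of the interval without ganaxolone = 17 / study week.

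| Visit | Weeks from double-blind baseline | Without ganaxolone | On ganaxolone | Share without |
|---|---|---|---|---|
| 6 | 21 | 17 | 4 | 17/21 = 81% |
| 7 | 36 | 17 | 19 | 17/36 = 47% |
| 8 | 52 | 17 | 35 | 17/52 = 33% |
| 9 | 68 | 17 | 51 | 17/68 = 25% |

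**Number affected.** About 25 subjects randomised 1:1 gives 25/2, or about 12 former placebo subjects if all enter the open-label phase.

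**Is a pre-ganaxolone value available?** Protocol 7.2.3 lists vital signs with weight, ECG, laboratory tests and urinalysis at Visit 5. Protocol 6.2.3.2 starts open-label dosing at the end of that visit, so these values precede the first ganaxolone dose. Measured from Visit 5, the intervals become 4, 19, 35 and 51 weeks, all on ganaxolone.

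**Height is the exception.** Protocol 7.6.2 takes it at screening and next at Week 36. With a 12-week baseline, the untreated span is 12 + 17 = 29 of 36 + 12 = 48 weeks at Week 36 (60%). With the 8-week baseline of earlier enrolees, it is 25 of 44 (57%). No Week 17 height exists.

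**Illustration for weight.** The documents give no growth rates. Assume 2 to 5 kg per year:
- 17 weeks gives 2 × 17/52 = 0.65 kg to 5 × 17/52 = 1.6 kg;
- the 4 ganaxolone weeks to Week 21 give 2 × 4/52 = 0.15 kg to 5 × 4/52 = 0.4 kg.

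Under that assumption, most of the growth-related weight change at Week 21 predates ganaxolone.

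**The case against.** Much can be said for the plan.

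- **Visit 5 is used.** A reader might infer that it is ignored. It is a scheduled double-blind visit, and its values, changes and laboratory shifts appear in the double-blind tables. Open-label tables are also split by double-blind arm and the data are listed, so about 12 girls could be reviewed one by one. This stands. What is missing is a summary that starts at ganaxolone.
- **ECG has no shift table.** A reader might expect a QTc abnormality that arose on placebo to appear as an open-label shift. Only laboratory tests get shift tables. ECG gets change values, interpretation counts by visit and the 60 msec criterion.
- **The contrast with adverse events is limited.** A reader might infer that pooled whole-study laboratory tables contradict the adverse event rule. Pooling over the whole study is planned only for exposure and adverse events. No whole-study laboratory, vital-sign or ECG table is described.
- **The percentages are time, not bias.** ALT, QTc and blood pressure do not accumulate with weeks, so 81% is not the share of a change that is misattributed. Several laboratory flags, such as those for bilirubin, AST, ALT and creatinine, are multiples of the upper limit of normal and need no baseline.
- **Simply replacing the baseline would create another fault.** Pooling by study week would then mix 21 with 4 weeks of ganaxolone at Week 21, and 36 with 19 at Week 36. The common baseline at least keeps elapsed time equal across arms.
- **Open-label results are descriptive** (SAP 7.2), and no test depends on them.

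These points reduce the harm and shape the remedy. None gives a reason why the former-placebo arm should have no open-label summary measured from its own start of ganaxolone.

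**Conclusion.** The point holds within limits. Both documents fix the baseline before double-blind dosing and neither makes an exception. In the former-placebo and combined open-label columns, laboratory, vital-sign and ECG changes, laboratory shifts and baseline-dependent flags therefore carry 17 weeks without ganaxolone, from 81% of the interval at Week 21 down to 25% at Week 68.

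This rests on nominal visit weeks, on full rollover for the count of about 12, and on reading pre-Rx, which the SAP does not define, as the SAP 9 baseline.

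The documents do not show that any safety conclusion is biased by a known amount. The tables are labelled as change from baseline, so reading them as change on ganaxolone is an inference, though a natural one in a phase described as all on drug. The double-blind baseline is right for the ganaxolone arm, for double-blind safety and for all seizure endpoints. Adverse events are unaffected. The change is worth making because it uses data already collected and serves a stated objective.

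**What to change.** In SAP 2.1 and 9, add a second baseline for open-label laboratory tests, vital signs except height, and ECG: the last value before the first ganaxolone dose. This is Visit 2 for the ganaxolone arm, where it equals the existing baseline, and pre-dose Visit 5 for the placebo arm.

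- Use it for the former-placebo arm's change summaries, laboratory shift tables and baseline-dependent flags, and state which baseline pre-Rx means.
- Index any column combined over arms by time since first ganaxolone. Among open-label visits, the placebo arm's 19, 35 and 51 weeks then sit beside the ganaxolone arm's 21, 36 and 52. The placebo arm's 4-week visit has no open-label counterpart and should stand alone. ECG, taken at Weeks 21 and 52, gives 4 and 35 weeks against 21 and 52, so it is better left uncombined at those visits.
- Keep the double-blind-baseline tables alongside, so that the Protocol 9.7 sentence can stand. Keep that baseline for double-blind safety and all seizure endpoints.
- Footnote that height cannot be re-anchored, because it is not measured between screening and Week 36, and that growth while on ganaxolone remains in the weight changes.

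The cost is one derived variable and a few extra descriptive tables, with no new data. SAP 10 analyses open-label data separately from the double-blind lock, and SAP 11 provides for later changes by SAP amendment.
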